3 INVESTIGATIONAL PLAN

3.1 General Schema of Study Design

This is a 3-arm, mixed methods, hybrid design trial. We expect to enroll up to 65 family units to produce at least 50 evaluable family units that are randomized to participate in one of the following intervention groups:

- Usual Care (n=10)
- DECIDES (n=20)
- DECIDES + coach (n=20)

3.1.1 Participant Identification

Oncology health care providers and the psychosocial services team in the Division of Oncology at the Children's Hospital of Philadelphia will assist in the identification of AYA patients with newly diagnosed or relapsed leukemia/lymphoma, solid tumors, or brain tumors who are within six weeks of diagnosis/relapse. Potentially eligible AYA patients will be referred to the DECIDES study team to assess eligibility criteria. If applicable, eligible AYA and their caregiver(s) will be contacted for enrollment. Oncology health care providers of enrolled AYA and caregiver(s) will also be invited to enroll in the study.

3.1.2 Intervention Groups

Family units of AYA and caregiver(s) are randomized (after the completion of baseline assessment) to participate in Usual Care (access to oncology health care providers for information and education), DECIDES (usual care plus independent access to website), or DECIDES + coach (usual care plus coach-supported access to website).

Oncology health care providers that enroll in the study are not randomized to participate in the intervention.

3.1.3 Assessment Time Points

All AYA and caregiver(s) that enroll to participate in the study will complete an electronic baseline assessment at time of enrollment (prior to randomization) and again at post-intervention (i.e., approximately six-weeks after date of randomization). Additionally, AYA and caregiver(s) randomized to DECIDES or DECIDES + coach will also complete an audio or video-recorded semi-structured qualitative interview with a member of the study team via Microsoft Teams after the post-intervention assessment.

Oncology health care providers of enrolled AYA and caregiver(s) will be invited to preview the DECIDES website, participate in an electronic rating scale and complete an audio-recorded semi-structured qualitative interview with a member of the study team via Microsoft Teams.

3.2 Study Duration, Enrollment and Number of Sites

3.2.1 Duration of Study Participation

Study participation is expected to last approximately two months for AYA and caregiver(s), beginning at the time of consent.

Study participation is expected to last approximately 30-45 minutes for oncology health care providers, beginning at the time of consent.

3.2.2 Total Number of Study Sites/Total Number of Subjects Projected

This study will be conducted at the Children's Hospital of Philadelphia and will enroll up to 65 family units of (1) AYA alone [≥ 18 years old], (2) Dyads [AYA ages 15-24 years old + Primary Caregiver], or (3) Triads [AYA ages 15-24 years old + Primary Caregiver + Second Caregiver]. We expect to produce at least 50 evaluable family units.

We will approach all oncology health care providers of enrolled AYA and caregiver(s) for participation in the study and expect to enroll approximately 25 of them. Oncology health care providers that have multiple AYA/caregiver(s) enrolled will only be asked to participate once in the study procedures.

3.3 Study Population

The study will include:

- AYA (ages 15-24 years) newly diagnosed or relapsed with cancer that are receiving treatment for a leukemia/lymphoma, solid tumor, or brain tumor in the Division of Oncology of the Children's Hospital of Philadelphia, and their caregiver(s) (primary and secondary, if applicable). AYA that are 18 and older may participate without a caregiver.
- Oncology health care providers that participate in decision-making about cancer treatment with enrolled AYA and caregiver(s).

3.3.1 Inclusion Criteria

AYA

- 1) Ages 15-24 years old.
- 2) Newly diagnosed or relapsed with a leukemia/lymphoma, solid tumor, or brain tumor within six weeks of study enrollment.
- 3) Ability to read and speak English.
- 4) If <18 Years Old: Parental/guardian permission to participate (informed consent).

CAREGIVER

- 1) Parent or Legal Guardian of a participating AYA.
- 2) Ability to read and speak English.

ONCOLOGY HEALTH CARE PROVIDER

- 1) Oncology health care provider involved in decision-making about cancer treatment with enrolled AYA patients and caregiver(s).
- 2) Ability to read and speak English.

3.3.2 Exclusion Criteria

AYA

- 1) Inability to read or speak English.
- 2) Pre-existing cognitive deficits (based on provider assessment) that result in impaired reading or decision-making capacity (i.e., developmental disability).
- 3) AYA patient is a ward of the state or any other agency, institution, or entity.
- 4) If <18 Years Old: No Parental/Guardian permission to participate (informed consent).

CAREGIVER

- 1) Foster parent or child advocate (i.e., caregiver is not biological parent or legal guardian).
- 2) Inability to read or speak English.

ONCOLOGY HEALTH CARE PROVIDER

- 1) Oncology health care provider that is not involved in decision-making about cancer treatment with enrolled AYA patients and caregiver(s).
- 2) Inability to read or speak English.

Subjects that do not meet all of the enrollment criteria may not be enrolled. Any violations of these criteria must be reported in accordance with IRB Policies and Procedures.

4 STUDY PROCEDURES

4.1 AYA and Caregiver(s)

4.1.1 Participant Identification

Health care providers and the psychosocial services team in the Division of Oncology at the Children's Hospital of Philadelphia will assist in the identification of potentially eligible patients newly diagnosed with leukemia/lymphoma, solid tumor, or brain tumor during weekly team meetings. Potentially eligible AYA patients will be referred to the DECIDES study team. If AYA and caregiver(s) meet all eligibility criteria, they will be invited to participate in the study. Informed consent/assent for participation will be obtained by phone or in-person during an outpatient oncology clinic visit or inpatient hospital stay.

4.1.2 Baseline Assessment (T1)

After providing informed consent/assent to participate in the study, AYA and caregiver(s) will complete an electronic baseline assessment via REDCap. The assessment will be completed either in-person on an iPad during an outpatient oncology clinic visit or inpatient hospital stay, or a link to the REDCap assessment will be emailed to participants to complete remotely (if needed).

4.1.3 Assignment to Intervention Group

Following completion of the baseline assessment, AYA and caregiver(s) will be randomly assigned to participate in one of the following conditions:

Usual Care

AYA and caregiver(s) assigned to participate in the Usual Care group will have access to their oncology health care providers and other members of the health care team for questions related to cancer and cancer treatment (as per usual).

DECIDES

In addition to usual care, AYA and caregiver(s) assigned to participate in the DECIDES group will receive a flyer that includes goals of the decision support intervention and instructions for accessing the DECIDES website. AYA and caregiver(s) will receive a text message reminder to review DECIDES, and the oncology health care provider will be informed of enrollment and the value clarification exercise results.

DECIDES + coach

In addition to usual care, AYA and caregiver(s) assigned to participate in the DECIDES + coach group will work with a coach (clinical research coordinator for this study) to review the DECIDES website in-person. The coach will guide the value clarification exercise with AYA and caregiver(s) separately and together. AYA and caregiver(s) will receive a text message reminder to review DECIDES, and the oncology provider will be informed of enrollment and the value clarification exercise results.

4.1.4 Post-Intervention Assessment (T2)

All AYA and caregiver(s) (assigned to Usual Care, DECIDES, or DECIDES + coach) will complete an electronic post-intervention assessment via REDCap. The assessment will be completed either in-person on an iPad during an outpatient oncology clinic visit or inpatient hospital stay, or a link to the REDCap assessment will be emailed to participants to complete remotely (if needed).

4.1.5 Semi-Structured Qualitative Interview (T3)

AYA and caregiver(s) (assigned to DECIDES or DECIDES + coach) will complete an audio or video-recorded semi-structured interview remotely via Microsoft Teams with a member of the study team.

4.2 Oncology Health Care Providers

4.2.1 Electronic Rating Scales

Oncology health care providers of enrolled AYA and caregiver(s) will preview the DECIDES website and complete the Systems Usability Scale (SUS)^(36,71). This will be emailed to them to complete remotely or can be administered remotely by a member of the study team during the semi-structured qualitative interview.

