2 STUDY OBJECTIVES

2.1 Primary Objective (or Aim)

The primary objective of this study is to assess the acceptability and feasibility of DECIDES using mixed methods and use results to inform implementation strategies for future dissemination.

Hyp 1a. Based on AYA, caregiver(s), and oncology health care provider ratings, and usage analytics, DECIDES will be acceptable and feasible during treatment decision-making within 6 weeks of diagnosis.

Hyp 1b. Qualitative interviews with AYA and caregiver(s) (randomized to DECIDES and DECIDES + coach) and oncology health care providers will confirm acceptability and feasibility ratings and provide specific information regarding timing, utility, barriers/facilitators, ease of use, and modifications to DECIDES for future implementation.

Hyp 1c (exploratory). DECIDES + coach will be rated more usable than DECIDES alone.

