4.2.2 Semi-Structured Qualitative Interview

Oncology health care providers of enrolled AYA and caregiver(s) will complete an audio or video-recorded semi-structured interview remotely via Microsoft Teams with a member of the study team.

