5.2 Self-Report Measures

Demographics: Variables will be collected based on AYA and caregiver(s) self-report and review of the patients' electronic health record. Demographic variables include age, gender, race/ethnicity, education/work, health care, and family history.

Intensity of Treatment Rating Scale (ITR-3): The revised version of a reliable and valid method for classifying pediatric oncology treatment protocols. This scale, completed by a medical provider, categorizes the intensity of pediatric cancer treatment from least through most intensive based on treatment modality and stage/risk level for the patient. ⁽⁹⁹⁾

Acceptability of the Decision Aid: A study-team developed measure used to obtain acceptability ratings from AYA and caregiver(s) (assigned to DECIDES or DECIDES + coach only). This measure is based on The Ottawa Hospital's measure of acceptability ratings regarding comprehensibility of components of a decision aid, its length, pace, amount of information, balance in presentation of information about options, and overall suitability for decision making. ⁽⁶⁾

Systems Usability Scale (SUS): This is a cost-effective, 10-item scale that is widely used to obtain a reference score for participants' view of a product's usability. This scale includes 10 statements that are scored on a 5-point scale of strength of agreement. Final scores can range from 0 to 100, in which higher scores indicate better usability. AYA and caregiver(s) (assigned to DECIDES or DECIDES + coach only) and oncology health care providers will complete this scale. ^(36,71)

Control Preferences: This scale assesses patient decision-making preferences and roles (i.e., patient's preferred role [baseline] versus the role they actually played in making a treatment decision [post-intervention]). This scale has been adapted for use in this study to assess caregiver decision-making preferences and roles, as well (i.e., caregiver's preferred role of patient [baseline] versus the role the patient actually played in making a treatment decision [post-intervention]). Decision-making preferences and roles are evaluated using three categories: 1) patient led, 2) shared, or 3) oncologist/caregiver led. ^(74,75)

Physician Decision Making Scale: A 5-item scale that measures physician involvement in medical decision-making. Items are rated on a 3-point scale ranging from 1 ("Yes, definitely") to 3 ("No"). Higher scores reflect lower involvement in decision-making. ⁽¹⁰⁰⁾

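### For providers who take the optional in-interview route, the SUS is not separated from the interview meant to confirm it and may be open to courtesy bias

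*Combined protocol and SAP*

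**What the plan says.** Section 4.2.1 gives two routes for the provider SUS. One is by email, for the provider to fill in alone. Under the other, the scale "can be administered remotely by a member of the study team during the semi-structured qualitative interview". Section 4.2.2 describes that interview as a recorded "semi-structured interview remotely via Microsoft Teams with a member of the study team".

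The provider rating and the interview both serve the primary objective in Section 2.1. Hyp 1a reads: "Based on AYA, caregiver(s), and oncology health care provider ratings, and usage analytics, DECIDES will be acceptable and feasible". Hyp 1b says that interviews, including those with providers, "will confirm acceptability and feasibility ratings and provide specific information regarding timing, utility, barriers/facilitators, ease of use".

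Section 5.2 limits the acceptability measure to families; it is "used to obtain acceptability ratings from AYA and caregiver(s) (assigned to DECIDES or DECIDES + coach only". Table 1 agrees: providers appear against usability but not against acceptability. They also supply the treatment intensity rating (ITR-3), but that describes the patient's treatment. The SUS is therefore the only rating of DECIDES that providers give.

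For families, Section 4.1.4 says that they "will complete an electronic post-intervention assessment via REDCap", and Section 3.1.3 places their interview after that assessment.

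**The concern.** A usability score is most credible when the respondent gives it alone, before discussing the product with the people who developed it. The in-interview route removes that separation in two ways.

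First, the provider may rate the tool in the presence of a member of the team that developed it, who works at the same hospital. Some courtesy in the answers is plausible.

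Second, Hyp 1b treats the interview as a check on the ratings. If the rating is collected within the interview, each can influence the other, and agreement between them says less than agreement between two separate observations.

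At stake is how far the provider SUS, and its agreement with the provider interviews, can be relied on as one strand of the acceptability and feasibility evidence.

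**Working it through.** The plan states no figure on this point, so there is none to reproduce. The check is mainly a comparison of texts.

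**Families and providers side by side**

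| Feature | Families in the DECIDES arms | Providers |
|---|---|---|
| Ratings of DECIDES | Acceptability measure and SUS (5.2, Table 1) | SUS only (5.2, Table 1) |
| How the SUS is given | Electronic form in REDCap, on an iPad or by emailed link (4.1.4) | Emailed, or administered by a study-team member during the interview (4.2.1) |
| Order of rating and interview | Interview after the T2 assessment (3.1.3) | Not fixed |
| Interviewer | Study-team member (4.1.5) | Study-team member (4.2.2) |

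For providers the plan gives no rule for choosing the route, no position for the SUS within the interview, no record of which route was used, and no analysis by route. The order is not fixed for the emailed route either: nothing says that the form must be returned before the interview.

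**Where the score is used**

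Section 2.1 names provider ratings under Hyp 1a. Section 6.1, however, analyses Hyp 1a through the acceptability questionnaire, click behavior, participation rate and time to implementation. It mentions the SUS only under the exploratory Hyp 1c, summarized for the two DECIDES arms. Providers are not randomized (3.1.2), so they have no place in that summary. The provider SUS is covered only by the general statement in Section 6 that all measurements will be summarized.

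**Scale of a possible shift (illustration)**

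Inputs from the documents:
- about 25 providers (3.2.2);
- the SUS range: "Final scores can range from 0 to 100, in which higher scores indicate better usability" (5.2).

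Assumed, because the documents give no values:
- b, the rise in score under the in-interview route: 5 to 10 points;
- f, the share of providers using that route: 25% to 75%;
- the SD of the SUS: 10, 15 or 20 points.

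Shift in the provider mean = f × b:
- lowest corner: 0.25 × 5 = 1.25 points;
- middle: 0.50 × 7.5 = 3.75 points;
- highest corner: 0.75 × 10 = 7.5 points.

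95% CI half-width for the mean = t(0.975, 24) × SD/√25 = 2.064 × SD/5:
- SD 10: 4.1 points;
- SD 15: 6.2 points;
- SD 20: 8.3 points.

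The middle case (3.75) lies below all three half-widths. The highest corner (7.5) exceeds the half-width for SD 10 and SD 15 but not for SD 20. Whatever its size, a shift of this kind moves the whole interval, and the interval's width does not reveal it.

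**The case against.** The strongest case on the other side is that this is a small matter in a descriptive pilot. Several parts of it stand.

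- **The route is optional.** The emailed route does not put rating and interview in one session, and nothing says how many providers would use the other.
- **Little depends on the score.** There is no SUS threshold, no test on the provider SUS, and no planned comparison of providers with families. The two groups differ in exposure anyway: providers preview the site, while families use it for their own decision.
- **The interview is an imperfect check on either route.** The same person rates and is interviewed, and a study-team member conducts every interview. Courtesy in the interview itself would remain after the fix; only the rating can be protected.
- **Hyp 1b speaks of acceptability and feasibility ratings, while the SUS measures usability.** The link still holds, because the SUS is the only provider rating available to confirm and Section 6.1 includes usability in the qualitative evaluation.
- **Some protection of candour exists.** Section 8.7 assures providers that participation will not affect employment or evaluation and that supervisors will not see their responses. It does not address frankness toward the study team.

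A reader might also infer two things that the documents do not support. One is that the items will be read aloud. The text says only that the scale is administered, Section 3.1.3 and the heading of 4.2.1 call it electronic, and a provider filling in a form during the call would fit the wording equally well. The other is that the in-interview route will go to providers who did not return the email, so that any bias follows non-response. Section 4.2.1 offers the two routes as alternatives and states no such rule.

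**Conclusion.** The point holds in a limited form. Section 4.2.1 permits the only provider rating of DECIDES to be collected by the study team inside the interview that is meant to confirm it. For providers who take that route, the rating may be open to courtesy bias and is not separated from the interview, whereas family ratings are completed electronically beforehand.

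It would be tempting to conclude that the primary acceptability and feasibility result is inflated, or that the bias matches the sampling error. Neither follows. The documents contain no mode effect, no share of providers per route and no SUS SD, and the shift passes the CI half-width only toward the upper end of the assumed values. The effect is confined to a descriptive SUS summary for about 25 non-randomized providers and to how its agreement with their interviews is read. This is an inexpensive improvement, not a flaw that threatens the trial.

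**What to change.** Reword Section 4.2.1 to say that:

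- each provider self-completes the SUS electronically through REDCap, after the website preview and before the interview;
- if the form has not been returned, the link is sent at the start of the Teams call, and the provider enters and submits the answers unseen by the interviewer, before discussion and recording begin;
- the mode and timing of completion are recorded for each provider.

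The fallback keeps the practical benefit of the in-call option, so little response should be lost. If the sponsor prefers to keep the present option, recording the mode and reporting the provider SUS by mode is the minimum.

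The cost is a change of wording plus two recorded items per provider. REDCap and Teams are already in use, and the form has 10 items. The downside is possibly one or two unreturned forms.

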4.2.2 Semi-Structured Qualitative Interview

Oncology health care providers of enrolled AYA and caregiver(s) will complete an audio or video-recorded semi-structured interview remotely via Microsoft Teams with a member of the study team.

4.3 Subject Completion/Withdrawal

Subjects may withdraw from the study at any time without prejudice to their care. The study team will document whether or not each subject completes the study.

5 STUDY EVALUATIONS AND MEASUREMENTS

5.1 Electronic Health Record Review

Medical information will be abstracted from the AYA patients' electronic health record (EPIC) for the following purposes:

- Enrollment Decision
- Demographics
- Diagnosis, date of diagnosis, age at diagnosis
- Intensity and types of treatments received (Using the Intensity of Treatment Rating-III)

5.2 Self-Report Measures

Demographics: Variables will be collected based on AYA and caregiver(s) self-report and review of the patients' electronic health record. Demographic variables include age, gender, race/ethnicity, education/work, health care, and family history.

Intensity of Treatment Rating Scale (ITR-3): The revised version of a reliable and valid method for classifying pediatric oncology treatment protocols. This scale, completed by a medical provider, categorizes the intensity of pediatric cancer treatment from least through most intensive based on treatment modality and stage/risk level for the patient. ⁽⁹⁹⁾

Acceptability of the Decision Aid: A study-team developed measure used to obtain acceptability ratings from AYA and caregiver(s) (assigned to DECIDES or DECIDES + coach only). This measure is based on The Ottawa Hospital's measure of acceptability ratings regarding comprehensibility of components of a decision aid, its length, pace, amount of information, balance in presentation of information about options, and overall suitability for decision making. ⁽⁶⁾

Systems Usability Scale (SUS): This is a cost-effective, 10-item scale that is widely used to obtain a reference score for participants' view of a product's usability. This scale includes 10 statements that are scored on a 5-point scale of strength of agreement. Final scores can range from 0 to 100, in which higher scores indicate better usability. AYA and caregiver(s) (assigned to DECIDES or DECIDES + coach only) and oncology health care providers will complete this scale. ^(36,71)

Control Preferences: This scale assesses patient decision-making preferences and roles (i.e., patient's preferred role [baseline] versus the role they actually played in making a treatment decision [post-intervention]). This scale has been adapted for use in this study to assess caregiver decision-making preferences and roles, as well (i.e., caregiver's preferred role of patient [baseline] versus the role the patient actually played in making a treatment decision [post-intervention]). Decision-making preferences and roles are evaluated using three categories: 1) patient led, 2) shared, or 3) oncologist/caregiver led. ^(74,75)

Physician Decision Making Scale: A 5-item scale that measures physician involvement in medical decision-making. Items are rated on a 3-point scale ranging from 1 ("Yes, definitely") to 3 ("No"). Higher scores reflect lower involvement in decision-making. ⁽¹⁰⁰⁾

Shared Decision-Making Questionnaire (SDM-Q-9): This is a brief, valid, and reliable 9-item questionnaire that measures the degree to which patients are involved in the process of decision-making (for preference-sensitive decisions, in which there are several treatment options for a particular disease) from the perspective of the patient. The SDM-Q-Doc (Physician Version) has been adapted for use in this study to measure the degree to which patients are involved in the process of decision-making from the perspective of the caregiver. Items are scored on a 6-point scale ranging from "completely disagree" (0) to "completely agree" (5), and a total sum score is calculated (ranging in values between 0-45). ⁽⁹⁴⁾

Adolescent and Young Adult Health Outcomes and Patient Experiences (AYA HOPE) Survey: Information needs are assessed using thirteen items from the AYA HOPE study survey. Participants indicate if they need more information on a range of topics related to cancer medical care and support services. The response options ("I need some more information" and "I need much more information" are collapsed and categorized as "unmet information need"; while the response options "I have enough information" and "Does not

apply" are collapsed and categorized as "met information need". Unmet information need (count) is categorized as low (0-3), intermediate (4-8), or high (9-13).^(76,77)

Knowledge of Clinical Trials: This is a 25-item true/false rating assessment used to assess participant understanding of clinical trials and informed consent processes.⁽⁶⁴⁾

Pediatric Research Participation Questionnaire (PRPQ): The PRPQ is a 12-item questionnaire for AYA (age 15-29) and caregivers (of AYA) about participation in a clinical trial. Items are rated on a 5-point scale, ranging from "not at all" (1) to "extremely" (5).^(15,16)

Decisional Conflict Scale: This is a valid and reliable 16-item scale, delivered in statement format (Version A), that measures personal perceptions of: uncertainty in choosing options; modifiable factors contributing to uncertainty (i.e., feeling uninformed, unclear about personal values, and supported in decision making); and effective decision making (i.e., feeling the choice is informed, values-based, likely to be implemented, and expressing satisfaction with the choice). Items are rated on a 5-point scale ranging from "strongly agree" (0) to "strongly disagree" (4). Higher scores indicate higher decisional conflict.

Satisfaction with Decision Scale: This is a valid and reliable 6-item instrument that measures patient satisfaction with a health care decision. The scale provides an efficient measure to evaluate decision-assisting technologies or patient-provider interactions aimed at involving patients in decision-making. Higher scores indicate higher satisfaction with the decision that was made.⁽⁶⁶⁾

Decision Self-Efficacy Scale: This is a valid and reliable 11-item instrument that measures self-confidence in one's abilities in decision-making (including shared decision-making). Items are rated on a 5-point scale, ranging from "not at all confident" (0) to "very confident" (4). Higher scores indicate higher self-efficacy.⁽⁶⁷⁾

Decision Regret Scale: This is a valid and reliable 5-item instrument that measures distress or remorse after a (health care) decision. Items are rated on a 5-point scale, ranging from strongly agree (1) to strongly disagree (5). Items 2 and 4 are reverse coded so that for each item, a higher score will indicate more regret.⁽⁷²⁾

PROMIS Profile: 25, 29, and Parent-Proxy The PROMIS measures assesses physical function mobility, depressive symptoms, fatigue, peer relationships, pain intensity, and pain interference. The PROMIS Pediatric Profile (25 items) is intended for use with those under age 18; the PROMIS Profile (29 items) is intended for use with those over age 18; and the PROMIS-Parent Proxy Profile (25 items) is a parent-report measure.⁽⁹⁶⁻⁹⁸⁾

Distress Thermometer: The Distress Thermometer is from the National Comprehensive Cancer Network (NCCN) Practice Guidelines in Oncology for Distress Management. It is an illustration (thermometer) used with patients to rate the number that best describes how much distress they have been experiencing in the past week, ranging from "no distress" (0) to "extreme distress" (10).

Affective Slider (AS): This is a digital self-reporting tool composed of two slider controls for the quick assessment of arousal (top) and pleasure (bottom) on a continuous scale. The

AS does not require written instructions. The scale is intentionally displayed using a neutral chromatic palette to avoid bias in rating (due to emotional connotation of colors). ⁽⁸⁷⁾

Affective Orientation (AO15): This is a valid and reliable 15-item measure used to assess how people use feelings and emotions to guide their behavior. Items are rated on a 5-point scale, ranging from strongly disagree (1) to strongly agree (5). Higher scores reflect greater awareness of emotions. ⁽⁸⁸⁾

Developmental Task Questionnaire (DTQ): The adolescent version of the DTQ is a 9-item self-report questionnaire that assesses adolescents' perceived developmental status; whereas the young adult version includes 8 items that assess developmental tasks for emerging adulthood. Items are rated on a 3-point scale ranging from "not yet started" (1) to "already developed" (3). Both adolescents and young adults are also asked to rank how important it is for them to achieve each of the normative developmental tasks on a 3-point scale, ranging from "not important" (1) to "very important" (3). ^(89,92)

Consideration of Future Consequences (CFC): This valid and reliable 12-item measure is used to assess the extent to which people consider distant versus immediate consequences of potential behaviors. Items are rated on a 5-point scale ranging from "extremely uncharacteristic" (1) to "extremely characteristic" (5). The CFC is scored so that higher numbers indicate a greater consideration of future consequences. ⁽⁹⁰⁾

Psychosocial Maturity Inventory (PMI): This is a 30-item self-report measure for AYA used to evaluate developmental aspects of maturity (i.e., self-reliance, self-concept, and work orientation). Items are rated on a 4-point scale, ranging from "agree strongly" (1) to "disagree strongly" (4). ⁽⁹⁵⁾

Emotion Regulation Questionnaire (ERQ): This is a valid and reliable 10-item measure used to assess processes of emotion regulation (cognitive reappraisal and expressive suppression). Items are rated on a 7-point scale ranging from "strongly disagree" (1) to "strongly agree" (7). The average score of items in the cognitive reappraisal subscale is calculated and the average score of items in the expressive suppression subscale is calculated. Higher scores indicate the greater use of that particular emotion regulation strategy, whereas lower scores indicate less frequent use. ⁽⁹¹⁾

Family Assessment Device (FAD): The Problem Solving subscale of the FAD includes 5 items that are rated on a 4-point scale ranging from "strongly agree" (1) to "strongly disagree" (4), with higher scores indicating more problematic functioning. ⁽⁹³⁾

